8.2 SAFETY AND OTHER ASSESSMENTS

The following additional procedures will be conducted to assess for respective safety outcomes and events:

- **Vital signs** (e.g., temperature, pulse, respirations, blood pressure). Vitals will be collected clinically per perioperative standards and protocols. These data will be collected and analyzed in relation to study drug administration, with particular focus on cardiovascular Adverse Events (AEs) (**See Section 9.4.4., Safety Analyses**).
- **Assessment of adverse events.** Assessment for Adverse Events (AEs) will occur throughout the study period (**Section 1.3, Schedule of Activities, SoA**) as described in following sections.
- **Baseline caffeine intake.** Habitual caffeine intake will be assessed among participants and categorized into no daily intake or any daily intake.
- **Baseline cognitive function.** Baseline cognitive function will be assessed via AD8 Dementia Screening Interview, Montreal Cognitive Assessment, and Cognitive Instrumental Activities of Daily Living.
- **Instrumental Activities of Daily Living.** Instrumental Activities of Daily Living will be assessed to determine preoperative functional status.
- **Postoperative nausea and vomiting.** Measured via the Postoperative Nausea and Vomiting Intensity Scale⁸⁹ in the PACU, postoperative day one afternoon, and postoperative day two afternoon. Any vomiting and antiemetic use from PACU admission through postoperative day two hours will also be recorded.
- **Arrhythmias.** Any new cardiac arrhythmia not previously experienced by the patient will be reported from PACU admission through postoperative day two.
- **Restraint use.** Any instance of restraint use related to altered mental status will be recorded.
- **Injury to self or others.** Any injury to self or others resulting from agitation/altered mental status
- **Falls.** Fall presence as reported by the patient, hospital staff, or medical record.

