4.3 JUSTIFICATION FOR DOSE

The study drug, either caffeine citrate or D5W (placebo), will be administered as an intravenous infusion starting at the beginning of surgical closure and again on the first two postoperative mornings. The infusion will be given over a 30-minute timespan. The two caffeine arms, 1.5 mg/kg and 3 mg/kg were carefully chosen based on preliminary data and literature review. Dosing will be based on total body weight.⁷²

The lower dose of 1.5 mg/kg may be appropriate for such an older population. First, the reduced dose might lower the risk of adverse side effects (e.g., nausea, vomiting, anxiety).³⁶ Second, our preliminary trial was based on a younger population (mean [\pm standard deviation] age [years]: 52 \pm 17), and the cognitive effects of caffeine may be more pronounced in older populations.⁷³ Lastly, serum caffeine concentration increases with age, as the total volume of caffeine distribution is reduced in older patients.⁷⁴ As such, higher peak serum caffeine concentrations are observed with advancing age after both intravenous and oral administration.⁷⁴

The higher dose of 3 mg/kg might provide added cognitive benefit.³⁷ In fact, the mean, weight-based dose for participants receiving caffeine *and not experiencing any delirium* in our preliminary trial was 3 mg/kg.²⁰ Additive cognitive benefit has also been observed with this dose, particularly for domains relevant to delirium (e.g., attention, vigilance)⁷⁵⁻⁷⁸ and after sleep deprivation,⁷⁹ which is commonly experienced in the hospital setting. Nonetheless, this higher dose may also be associated with additional side effects (e.g., anxiety, GI distress, nausea/vomiting), so multiple dosing arms will help to determine optimal perioperative doses that maximize benefit-to-risk ratios across each postoperative day.

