6 STUDY INTERVENTION

6.1 STUDY INTERVENTION(S) ADMINISTRATION

6.1.1 STUDY INTERVENTION DESCRIPTION

Participants will be block randomized with a 1:1:1 allocation ratio (placebo: low-dose caffeine: high-dose caffeine) in a three-arm parallel design. Prepared intravenous syringe solutions of D5W (placebo) or caffeine citrate will be directly delivered to the operating room prior to the surgery of enrolled participants. For the next two postoperative mornings, the study drug will be given with scheduled, morning medications as administered and overseen by the research nurse (or physician assistant).

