6.1.2 DOSING AND ADMINISTRATION

The study drug will be administered as an intravenous infusion, using an infusion pump, over 30 (±5) minutes beginning during surgical closure and on the first two postoperative mornings. Low-dose caffeine will consist of 1.5 mg/kg caffeine base, and high-dose caffeine will contain 3 mg/kg caffeine base; both caffeine drugs will be dissolved in 40 mLs of dextrose 5% in water. No dose or timing changes are anticipated, and the infusion will be administered over the entire 30 (±5) minutes. A research nurse or physician assistant will oversee the drug administration and monitor blood pressure (every 5 minutes), heart rate, heart rhythm (via 5-lead electrocardiography), and continuous pulse oximetry.

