9.4.4 SAFETY ANALYSES

Data will be reported on specific safety outcomes that may be related to caffeine. Despite the high safety profile associated with caffeine, certain risks have been associated with administration (see **Section 2.3, Risk/Benefit Assessment**). The following adverse events that may occur with caffeine will be reported:

Outcome	Measure
New cardiac arrhythmia (e.g., supraventricular tachycardia, ventricular tachycardia) incidence	Incidence (%)
SBP (mm Hg)*	n (SD)
DBP (mm Hg)*	n (SD)

The CAffeine, Postoperative Delirium, And CHange IN Outcomes after Surgery-2 (CAPACHINOS-2) Study Protocol <2.0>

Version <2.0>
<14 December 2022>

HR (BPM)*	n (SD)
Restraint use	Incidence (%)
Injury to self or others	Incidence (%)
Postoperative Nausea and Vomiting**	Score (n)
Dehydration†	Incidence (%)
Allergic Reaction‡	Incidence (%)

*Vitals will be presented as descriptive statistics – no cutoff thresholds will be assigned. **Via Postoperative Nausea and Vomiting Intensity Scale. †Dehydration will be recorded if this term is described in the medical record by clinical teams caring for the patient. ‡The nature of any suspected allergic reaction will be reported in full detail.

The study drug will be discontinued in the event of new-onset cardiac arrhythmia, suspected allergic reaction, or any other concern raised by either the clinical or research team. Adverse events will otherwise be coded as described in **Section 8.3, Adverse Events and Serious Adverse Events**.

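### The Section 8.2 arrhythmia window opens at PACU admission, after the first infusion has begun, and Sections 8.2, 8.3.4 and 9.4.4 imply different numerators for arrhythmia incidence

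*Protocol*

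**What the plan says.** The only text that gives the arrhythmia outcome a time window is Protocol Section 8.2: "Any new cardiac arrhythmia not previously experienced by the patient will be reported from PACU admission through postoperative day two".

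The first dose comes earlier than that. Section 4.3 has study drug given "starting at the beginning of surgical closure and again on the first two postoperative mornings", which makes three infusions. Section 6.1.2 gives the duration: "over 30 (±5) minutes beginning during surgical closure and on the first two postoperative mornings". Section 6.1.1 places the first one, since the syringes "will be directly delivered to the operating room prior to the surgery of enrolled participants". During administration, Section 6.1.2 requires monitoring that includes "heart rhythm (via 5-lead electrocardiography), and continuous pulse oximetry".

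Section 9.4.4 introduces its table with "The following adverse events that may occur with caffeine will be reported" and lists "New cardiac arrhythmia (e.g., supraventricular tachycardia, ventricular tachycardia) incidence", expressed as a percentage, with no start or end time. The same section says that study drug is stopped for new-onset arrhythmia, without limiting this to events after PACU arrival.

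Section 8.3.4 sets the general adverse event rules. Recording runs from consent to 7 days (non-serious) or 30 days (serious) after the end of participation. A condition present at screening is baseline, but its deterioration is an adverse event. Arrhythmia history is not among the 12 exclusion criteria in Section 5.2.

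**The concern.** A drug-safety outcome would normally begin at first exposure. Here the defined window begins at a change of location, after first exposure has started. An arrhythmia that halts the first infusion and resolves before the patient leaves the operating room would meet the Section 9.4.4 stopping criterion and yet fall outside the Section 8.2 outcome.

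The sections are also not tied together. Section 9.4.4 does not say whether its arrhythmia line uses the Section 8.2 window or the wider adverse event window of Section 8.3.4. Two analysts could each follow the protocol and report different incidences. Section 4.3 says that the two dose arms are there to weigh benefit against risk, and Section 10.1.6 names arrhythmias among the data the DSMB will review. An ambiguous numerator affects both uses.

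**Working it through.** The plan states no figure for this outcome, so there is none to reproduce. The check is a comparison of the sections, plus one count.

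**Order of events on the day of surgery**

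1. Surgical closure begins and the first infusion starts (Sections 4.3 and 6.1.2), in the operating room (Section 6.1.1).
2. The infusion runs for 25 to 35 minutes (30 ± 5, Section 6.1.2).
3. The patient is admitted to the PACU and the Section 8.2 window opens.

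Step 1 always precedes step 3. The protocol gives no interval from closure to PACU admission, so it does not establish whether step 2 has finished by then.

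**How each section treats a given event**

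| Event | 8.2 outcome | 8.3.4 adverse event | 9.4.4 table line |
|---|---|---|---|
| New arrhythmia, starts and resolves in the operating room during infusion 1 | Outside | Recorded | Not determined (no window) |
| New arrhythmia, starts in the operating room and persists into the PACU | Not stated | Recorded | Not determined |
| New arrhythmia in the operating room that resolves and returns in the PACU | Read literally, already experienced | Recorded | Not determined |
| New arrhythmia between PACU admission and the end of postoperative day two | Counted | Recorded | Counted |
| New arrhythmia on postoperative day three | Outside | Recorded | Not determined |
| Different arrhythmia type in a patient with a history | Counted if in the window | Recorded | Counted if in the window; otherwise not determined |
| Recurrence of the patient's known arrhythmia | Outside | Recorded if a deterioration | Outside (new only) |

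The first row shows the gap at first exposure. The "not determined" entries show the missing link between sections. The third row arises because 8.2 does not say what reference time decides whether an arrhythmia is new.

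**Count of infusions starting outside the window**

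- Inputs: 3 infusions per patient (Section 4.3), 250 participants (Section 9.2), 1:1:1 allocation (Section 4.1).
- Share of scheduled infusions: 1 / 3 = 33%.
- Per arm: 250 / 3 ≈ 83.3. First placebo infusions ≈ 83; first caffeine infusions ≈ 2 × 83.3 ≈ 167.

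This assumes that all 250 start the first infusion. It counts exposures, not events. The protocol gives no arrhythmia rate for any arm or period, so the number of arrhythmias affected cannot be derived.

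**The case against.** The strongest reply is that these arrhythmias are captured elsewhere. Adverse events are recorded from consent. Section 7.1 requires the time and reason for any discontinuation. Section 8.2 itself has vital signs analysed in relation to drug administration, with a focus on cardiovascular adverse events. The DSMB sees arrhythmia data unblinded. Section 9.4.4 presents its table as adverse events with no PACU limit, so an intraoperative arrhythmia could properly appear there. All of this stands as to recording. It does not settle the tabulated incidence, because Section 8.2 remains the only window attached to this outcome and nothing says that Section 9.4.4 overrides it.

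A reader might also infer four stronger things that the protocol does not support.

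- *Arrhythmias during the first infusion are lost.* They are not: they are adverse events under Section 8.3.4 and may be counted in Section 9.4.4.
- *Patients with an arrhythmia history can never contribute an event.* A different type counts as new, and a deterioration is an adverse event. Restricting the outcome to new arrhythmia is consistent between Sections 8.2 and 9.4.4 and is a legitimate choice of definition.
- *The first infusion is usually over before the window opens.* No timing is given to show this. Effects that appear after PACU admission are inside the window in any case.
- *The caffeine–placebo difference is biased towards no harm.* The same rule applies to all blinded arms. Such a bias would arise only if caffeine caused arrhythmias in the omitted period or in the omitted recurrences, and no figure in the protocol bears on that.

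**Conclusion.** The point holds in a limited form. As defined in Section 8.2, the arrhythmia outcome excludes a new arrhythmia confined to the operating-room part of the first infusion, a period in which rhythm is monitored and a new arrhythmia would stop the drug. Sections 8.2, 8.3.4 and 9.4.4 then allow different numerators for one reported incidence.

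In size, one of three scheduled infusions starts outside the window, about 167 on caffeine and 83 on placebo if all 250 participants are treated. The effect on the reported incidence is unknown and could be small. The conclusion rests on reading Section 8.2 as the operative definition for the Section 9.4.4 line, which is the natural reading because no other section gives that outcome a window. The correction is worth making because it is cheap and settles what is counted at first exposure. The limitation to new arrhythmia is not an error.

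**What to change.** - In Section 8.2, start the arrhythmia window at the start of the first infusion and keep the existing end point.
- Define new as not present or documented at the preoperative baseline, so that an arrhythmia first seen in the operating room remains new if it persists or returns in the PACU.
- In Section 9.4.4, state that the arrhythmia incidence uses this same window and is presented by arm. Wider adverse event capture under Section 8.3.4 can stay as it is.
- Optionally, add a separate descriptive line by arm for recurrent or worsened arrhythmia, since patients with a history are eligible.

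The cost is protocol wording and a CRF field for onset time relative to infusion; rhythm monitoring during administration is already required. The trade-off is that some arrhythmias of surgical or anaesthetic origin will be counted in all arms, which adds background events to the comparison. No dose, schedule or stopping rule changes.

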8.3 ADVERSE EVENTS AND SERIOUS ADVERSE EVENTS

8.3.1 DEFINITION OF ADVERSE EVENTS (AE)

Adverse event means any untoward medical occurrence associated with the use of an intervention in humans, whether or not considered intervention-related (21 CFR 312.32 (a)).

8.3.2 DEFINITION OF SERIOUS ADVERSE EVENTS (SAE)

The CAffeine, Postoperative Delirium, And CHange IN Outcomes after Surgery-2 (CAPACHINOS-2) Study Protocol <2.0>

Version <2.0>
<14 December 2022>

An adverse event (AE) or suspected adverse reaction is considered "serious" if it results in any of the following outcomes: death, a life-threatening adverse event, inpatient hospitalization or prolongation of existing hospitalization, a persistent or significant incapacity or substantial disruption of the ability to conduct normal life functions, or a congenital anomaly/birth defect. Important medical events that may not result in death, be life-threatening, or require hospitalization may be considered serious when, based upon appropriate medical judgment, they may jeopardize the participant and may require medical or surgical intervention to prevent one of the outcomes listed in this definition. Examples of such medical events include allergic bronchospasm requiring intensive treatment in an emergency room or at home, convulsions that do not result in inpatient hospitalization, or the development of drug dependency or drug abuse.

8.3.3 CLASSIFICATION OF AN ADVERSE EVENT

8.3.3.1 SEVERITY OF EVENT

The following guidelines will be used to describe AE severity:

- **Mild** – Events require minimal or no treatment and do not interfere with the participant's daily activities.
- **Moderate** – Events result in a low level of inconvenience or concern with the therapeutic measures. Moderate events may cause some interference with functioning.
- **Severe** – Events interrupt a participant's usual daily activity and may require systemic drug therapy or other treatment. Severe events are usually potentially life-threatening or incapacitating. Of note, the term "severe" does not necessarily equate to "serious."

8.3.3.2 RELATIONSHIP TO STUDY INTERVENTION

All adverse events (AEs) must have their relationship to study intervention assessed by the clinician who examines and evaluates the participant based on temporal relationship and his/her clinical judgment. The degree of certainty about causality will be graded using the categories below.

- **Definitely Related** – There is clear evidence to suggest a causal relationship, and other possible contributing factors can be ruled out. The clinical event, including an abnormal laboratory test result, occurs in a plausible time relationship to study intervention administration and cannot be explained by concurrent disease or other drugs or chemicals. The response to withdrawal of the study intervention (dechallenge) should be clinically plausible. The event must be pharmacologically or phenomenologically definitive, with use of a satisfactory rechallenge procedure if necessary.
- **Probably Related** – There is evidence to suggest a causal relationship, and the influence of other factors is unlikely. The clinical event, including an abnormal laboratory test result, occurs within a reasonable time after administration of the study intervention, is unlikely to be attributed to concurrent disease or other drugs or chemicals, and follows a clinically reasonable response on withdrawal (dechallenge). Rechallenge information is not required to fulfill this definition.
- **Potentially Related** – There is some evidence to suggest a causal relationship (e.g., the event occurred within a reasonable time after administration of the trial medication). However, other factors may have contributed to the event (e.g., the participant's clinical condition, other concomitant events). Although an AE may rate only as "possibly related" soon after discovery, it can be flagged as requiring more information and later be upgraded to "probably related" or "definitely related", as appropriate.

The Caffeine, Postoperative Delirium, And CHange IN Outcomes after Surgery-2 (CAPACHINOS-2) Study Protocol <2.0>

Version <2.0>
<14 December 2022>

- **Unlikely to be related** – A clinical event, including an abnormal laboratory test result, whose temporal relationship to study intervention administration makes a causal relationship improbable (e.g., the event did not occur within a reasonable time after administration of the study intervention) and in which other drugs or chemicals or underlying disease provides plausible explanations (e.g., the participant's clinical condition, other concomitant treatments).
- **Not Related** – The AE is completely independent of study intervention administration, and/or evidence exists that the event is definitely related to another etiology. There must be an alternative, definitive etiology documented by the clinician.]

8.3.3.3 EXPECTEDNESS

The Study PI ([name]) will be responsible for determining whether an adverse event (AE) is expected or unexpected. An AE will be considered unexpected if the nature, severity, or frequency of the event is not consistent with the risk information previously described for the study intervention.

8.3.4 TIME PERIOD AND FREQUENCY FOR EVENT ASSESSMENT AND FOLLOW-UP

The occurrence of an adverse event (AE) or serious adverse event (SAE) may come to the attention of study personnel during study visits and interviews of a study participant presenting for medical care, or upon review by a study monitor.

All AEs including local and systemic reactions not meeting the criteria for SAEs will be captured on the appropriate case report form (CRF). Information to be collected includes event description, time of onset, clinician's assessment of severity, relationship to study product (assessed only by those with the training and authority to make a diagnosis), and time of resolution/stabilization of the event. All AEs occurring while on study must be documented appropriately regardless of relationship. All AEs will be followed to adequate resolution.

Any medical condition that is present at the time that the participant is screened will be considered as baseline and not reported as an AE. However, if the study participant's condition deteriorates at any time during the study, it will be recorded as an AE.

Changes in the severity of an AE will be documented to allow an assessment of the duration of the event at each level of severity to be performed. AEs characterized as intermittent require documentation of onset and duration of each episode.

The study team will record all reportable events with start dates occurring any time after informed consent is obtained until 7 (for non-serious AEs) or 30 days (for SAEs) after the last day of study participation. At each study visit, the investigator will inquire about the occurrence of AE/SAEs since the last visit. Events will be followed for outcome information until resolution or stabilization.

All serious, unexpected, and probably related events must be reported to the study principal investigator, [name] ([contact]).

8.3.5 ADVERSE EVENT REPORTING

The study team will report Adverse Events (AEs) per guidelines and timetables set forth by University of Michigan Institutional Review Board (IRBMED). AEs will also be uploaded to the online data repository, the Research Electronic Data Capture (REDCap) system.

The CAffeine, Postoperative Delirium, And CHange IN Outcomes after Surgery-2 (CAPACHINOS-2) Study Protocol <2.0>

Version <2.0>
<14 December 2022>

8.3.6 SERIOUS ADVERSE EVENT REPORTING

The study clinician will immediately report to the sponsor any serious adverse event, whether or not considered study intervention related, including those listed in the protocol or investigator brochure and must include an assessment of whether there is a reasonable possibility that the study intervention caused the event. Study endpoints that are serious adverse events (e.g., all-cause mortality) must be reported in accordance with the protocol unless there is evidence suggesting a causal relationship between the study intervention and the event (e.g., death from anaphylaxis). In that case, the investigator must immediately report the event to the sponsor.

All serious adverse events (SAEs) will be followed until satisfactory resolution or until the site investigator deems the event to be chronic or the participant is stable.

8.3.7 REPORTING EVENTS TO PARTICIPANTS

Individual participants will be notified of any serious, unanticipated adverse events probably related to study interventions.

8.3.8 EVENTS OF SPECIAL INTEREST

Not applicable

8.3.9 REPORTING OF PREGNANCY

Pregnancy tests will not be ordered for this study, as only patients ≥ 70 years of age will be eligible.

